1.3 Schedule of Activities

Study Period	Screening	Intervention					Follow-up				Notes
Visit Number/Title	1	2	3	4	5	6	7	8	9	10	
Scheduled Day (Window)	Screening (≤ 48 hours before rand.) ^a	Day 1 ^b	Day 2	Day 3 ^c	Day 4	EOT	Day 10 (± 1 day)	Day 15 (+3 days)	Day 29 (+3 days)	LFU Month 7 (± 1 month) ^d	
Type of Visit	C	C	V/C	C	V/C	C	C	C	C	V	C = Clinic or At-home visit V= Virtual visit (when a virtual visit is listed, a clinic or home visit is not required. Virtual visits may be conducted at the investigator's discretion)
Administrative Procedures											
Informed Consent	X										
Informed Consent for FBR (Optional)	X										Informed consent for FBR should be presented at screening, however, if delayed, present at next possible visit as outlined in Appendix 6.
Informed Consent for PBMC Collection (Optional)	X										Only a subset of participants at selected sites
Register Study Visit in IRT	X	X									
Inclusion/Exclusion Criteria	X ^e	X ^f									Including review of SARS-CoV-2 (+) local test results ^g
Participant Identification Card	X	X									Randomization number must be added to card at randomization
Medical History	X	X									Including day of onset of COVID-19 signs/symptoms
Prior/Concomitant Medication Review	X	X	X	X	X	X	X	X	X		Including COVID-19 standard of care therapies and supportive care
Intervention Randomization		X ^b									COVID-19 severity categorization entered in IRT at randomization must be based on values obtained on Day 1 prior to randomization

Study Period	Screening	Intervention					Follow-up				Notes
		1	2	3	4	5	6	7	8	9	10
Visit Number/Title	1										
Scheduled Day (Window)	Screening (≤ 48 hours before rand.) ^a	Day 1 ^b	Day 2	Day 3 ^c	Day 4	EOT	Day 10 (± 1 day)	Day 15 ($+3$ days)	Day 29 ($+3$ days)	LFU Month 7 (± 1 month) ^d	
Collect/Update Secondary Contacts for Participant	X			X		X		X	X		
MK-4482 or Placebo Administration		X	X	X	X	X					All efforts should be made to administer the first dose on Day 1 (randomization), but administration of the first dose must be within 24 hours of randomization
MK-4482 or Placebo – Observed Dosing						X					The morning dose at EOT will be observed to facilitate PK blood collection.
Dispense Study Intervention and Participant Study Supplies		X									Including participant diaries
Completion of Study Medication Diary		X	X	X	X	X					

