6.3.2 Stratification

Intervention randomization will be stratified according to the following factors:

Part 1

1. Time from symptom onset prior to the day of randomization (≤ 5 days, >5 days)
2. At increased risk of severe illness from COVID-19 (Appendix 10) (yes, no)

Based on the viral kinetics of SARS-CoV-2 and the mechanism of action of MK-4482, treatment with antiviral therapy is likely to have a greater benefit with earlier treatment (≤ 5 days) rather than later treatment (>5 days). In addition, certain characteristics or underlying medical conditions (Appendix 10) have been identified that place patients at increased risk for severe illness from COVID-19, which may result in hospitalization, ICU-level care, ventilatory support, or death. The selection of these criteria as stratification factors will help ensure that the treatment groups will be well balanced within each stratum and the study results will not be confounded by factors suspected to have a potential impact on a participant's response to study intervention.

Of note, at least 75% of participants overall must have at least 1 characteristic or underlying medical condition associated with being at increased risk for severe illness from COVID-19 as defined in Appendix 10. In addition, enrollment of participants with moderate COVID-19 (Appendix 9) will be limited to 50% of total planned sample size.

Part 2

1. Time from symptom onset prior to the day of randomization (≤ 3 days, >3 days)

Based on updates to inclusion criterion #2 wherein the initial onset of signs/symptoms attributable to COVID-19 was amended to ≤ 5 days prior to the day of randomization to target participants earlier in their COVID-19 disease course, the time from symptom onset prior to the day of randomization stratification factor was amended to ≤ 3 days or >3 days. Based on the viral kinetics of SARS-CoV-2 and the mechanism of action of MK-4482, treatment with antiviral therapy is likely to have a greater benefit with earlier treatment (≤ 3 days) rather than later treatment (>3 days).

Of note, all participants must have at least 1 characteristic or underlying medical condition associated with being at increased risk for severe illness from COVID-19 as defined in

Appendix 10. Age is a risk factor independent of other health conditions, so while there is no minimal enrollment for participants >60 years of age, every effort should be made to maximize enrollment of this age group.

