9.4.1 Efficacy/Pharmacokinetics Endpoints

9.4.1.1 Efficacy Endpoints

Primary:

- Proportion of participants with either hospitalization (≥ 24 hours of acute care in a hospital or similar acute care facility, including emergency rooms or facilities created to address hospitalization needs during the COVID-19 pandemic) or death by Day 29.

Secondary:

- Time to sustained resolution or improvement of each targeted self-reported sign/symptom present at randomization (ie, Day 1), defined as the number of days from randomization to the first of 3 consecutive days when resolution or improvement is demonstrated for each targeted self-reported sign/symptom. Participants who meet criteria for sustained resolution or improvement after 3 consecutive days must not relapse by Day 29 (ie, have 2 or more consecutive days of each self-reported sign/symptom returning to the baseline severity or worse than baseline severity after the criteria for sustained resolution or improvement are met). Resolution or improvement is defined as follows:
 - A symptom reported at randomization as Mild and is subsequently reported as None
 - A symptom reported at randomization as Moderate and is subsequently reported as Mild or None,
 - A symptom reported at randomization as Severe and is subsequently reported as Moderate, Mild or None
 - A symptom reported at randomization as Yes and is subsequently reported as No

NOTE: Participants without a symptom reported at randomization will not be included in the analysis

- Time to progression of the targeted self-reported signs/symptoms present at randomization, defined as the number of days from randomization to the first of

2 consecutive days when the targeted self-reported signs/symptoms worsen.
Worsening is defined as follows:

- A symptom reported at randomization as None or No and is subsequently reported as Mild/Moderate/Severe or Yes, respectively
- A symptom reported as Mild at randomization and is subsequently reported as Moderate or Severe
- A symptom reported as Moderate at randomization and is subsequently reported as Severe

NOTE: Participants with symptoms reported at randomization as Severe will not be included in the analysis

- Odds of a more favorable response on the WHO 11-point ordinal scale on Day 3, EOT, Day 10, Day 15, and Day 29. This scale provides a measure of illness severity across a range from 0 (not infected) to 10 (dead).

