Note: Relevant data (ie, central laboratory SARS-CoV-2 RNA results, supplemental oxygen use and methods, oxygen saturation, dialysis and vasopressor use, vital status, and investigator assessment of the participant's ability to independently perform daily activities with minimal or no symptoms) to support determination of the WHO 11-point ordinal score will be collected in eCRFs.

Exploratory:

- Percentage of participants who have any acute care visit. Acute care visit is defined as any hospitalization (any amount of time in a hospital or similar acute care facility, including emergency rooms or facilities created to address hospitalization needs during the COVID-19 pandemic) or emergency room visit or any other acute care visit (including an urgent care visit or visit with any healthcare provider for acute care needs) from randomization through Day 29
- Percentage of participants who have any COVID-19-related acute care visit. Acute care visit is defined as any hospitalization (any amount of time in a hospital or similar acute care facility, including emergency rooms or facilities created to address hospitalization needs during the COVID-19 pandemic) or emergency room visit or any other acute care visit (including an urgent care visit or visit with any healthcare provider for acute care needs) from randomization through Day 29
- Change from baseline in SARS-CoV-2 RNA titer in nasopharyngeal and oropharyngeal swabs separately at various timepoints
- Percentage of participants with undetectable SARS-CoV-2 RNA in nasopharyngeal and oropharyngeal swabs separately at various timepoints

- Viral RNA mutation rate and detection of treatment-emergent sequence variants as assessed by comparison of baseline and post-baseline virus sequencing
- Percentage of participants with undetectable infectious SARS-CoV-2 in nasopharyngeal swabs on Day 3, EOT, Day 10, Day 15, and Day 29.

In addition to the endpoints listed above, survival, supplemental oxygen use, and hospitalization status at the LFU visit (Month 7) will also be summarized.

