The viral RNA endpoints at earlier time points (Day 3 and EOT) will be important for the dose selection decision from Part 1 of the study. Change from baseline in SARS-CoV-2 RNA titer, calculated as \log_{10} (post) minus \log_{10} (baseline), as measured by quantitative RT-PCR of samples from NP (Parts 1 and 2) and OP (Part 1 only) swabs will be summarized separately by treatment group and time point. The DAO approach will be used to handle missing data for these summary statistics. In addition to summary statistics, treatment differences in change in SARS-CoV-2 RNA titer from baseline over time will be estimated using longitudinal models. Graphical presentations of the change from baseline will be presented and the impact of baseline viral RNA level will be explored using subgroup analyses (defined by level of baseline viral RNA) and analyses/summaries that exclude participants with low baseline levels (eg, viral RNA $<10^6$ copies/mL).

Percentage of participants with undetectable viral RNA (below limit of detection) as measured by qualitative RT-PCR of samples from NP (Parts 1 and 2) and OP (Part 1 only) swabs will be summarized separately by treatment group and time point. Between-treatment differences and 95% CIs will be estimated using the stratified Miettinen and Nurminen method [Miettinen, O. 1985].

WHO 11-point ordinal scale score will be analyzed using the cumulative logits function and the proportional odds model as described by McCullagh [McCullagh, P. 1980]. This methodology provides an estimate of the common odds ratio for assessing differences between treatment groups. In addition to a term for treatment group, the model will include terms for the stratification factors specified Section 6.3.2. The WHO 11-point ordinal scale will be determined based on relevant data collected in eCRFs.

A detailed analysis strategy for key efficacy endpoints is listed in [Table 5](#).

Table 5 Analysis Strategy for Key Efficacy Endpoints

Endpoint/Variable (Description, Time point)	Primary vs. Supportive Approach ^a	Statistical Method ^b	Analysis Population	Missing Data Approach
Primary				
Proportion of participants with either hospitalization or death by Day 29	P	Stratified Miettinen and Nurminen ^c	MITT	As described in 9.6.1
Proportion of participants with either hospitalization or death by Day 29	S	Stratified Miettinen and Nurminen ^c	PP	Observed data only

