Proportion of participants with either COVID-related hospitalization or death by Day 29	S	Stratified Miettinen and Nurminen ^c	MITT	M=F ^d
Proportion of participants with either COVID-related hospitalization or death by Day 29	S	Stratified Miettinen and Nurminen ^c	PP	Observed data only
Time to hospitalization or death by Day 29	S	Stratified log-rank test ^e ; Stratified Cox proportional hazard regression ^f	MITT, PP	Model-based with censoring
Time to COVID- related hospitalization or death by Day 29	S	Stratified log-rank test ^e ; Stratified Cox proportional hazard regression ^f	MITT, PP	Model-based with censoring
Secondary				
Time to sustained resolution or improvement of each targeted self-reported sign/symptoms of COVID-19	P (MITT) S (PP)	Stratified log-rank test ^e ; Stratified Cox proportional hazard regression ^f	MITT PP	Model-based with censoring
Time to progression of each targeted self-reported sign/symptom of COVID-19	P (MITT) S (PP)	Stratified log-rank test ^e ; Stratified Cox proportional hazard regression ^f	MITT PP	Model-based with censoring
Odds of a more favorable response on the WHO 11-point ordinal scale on Day 3, EOT, Day 10, Day 15, and Day 29	P (MITT) S (PP)	Proportional odds model ^g	MITT PP	Model-based
EOT= end of treatment; F= failure; M= missing; MITT= modified intent-to-treat; PP= per-protocol; WHO= World Health Organization.				
^a P=Primary approach; S=Supportive approach.				
^b Statistical models are described in further detail below:				
^c Miettinen and Nurminen method stratified by the factors specified in Section 6.3.2.				
^d M=F is Missing equals to Failure				
^e The stratified log-rank test includes stratification factors specified in Section 6.3.2				
^f Stratified Cox Proportional Hazards regression includes terms for treatment, stratification factors specified in Section 6.3.2				
^g Proportional odds model includes terms for treatment and stratification factors specified in Section 6.3.2.				

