10.9 Appendix 9: COVID-19 Severity Categorization

Adapted from “COVID-19: Developing Drugs and Biological Products for Treatment or Prevention Guidance for Industry” US Food and Drug Industry (MAY 2020), WHO COVID-19 case definition, and COVID-19 symptoms recognized by CDC [Food and Drug Administration 2020] [World Health Organization 2020] [Tenforde, M. W., et al 2020].

For inclusion in the study, the following are required of all participants:

- A **positive SARS-CoV-2 test** result (Inclusion Criterion #1)
- Signs/symptoms attributable to COVID-19 present at randomization (Inclusion Criterion #2), including one or more of the following: **fever >38.0°C, chills, cough, sore throat, shortness of breath or difficulty breathing with exertion, fatigue, nasal congestion, runny nose, headache, muscle or body aches, nausea, vomiting, diarrhea, loss of taste, loss of smell**

In addition to the above criteria, the participant must be categorized into one of the following COVID-19 severity categories at the time of randomization: **mild or moderate COVID-19** (Inclusion Criterion #3). The COVID-19 severity category that is entered in IRT at randomization must be based on assessments (vital signs, COVID-19 signs/symptoms, respiratory measures, oxygen therapy, ongoing medical history) completed and documented on Day 1 prior to calling IRT in order to randomize.

Vital sign measurements should be preceded by at least 5 minutes of rest for the participant in a quiet setting without distractions.

Mild COVID-19:

Must have **ALL** of the following:

- Respiratory rate <20 breaths per minute
- Heart rate <90 beats per minute
- SpO₂ >93% on room air or on supplemental oxygen for a reason other than COVID-19 which HAS NOT increased since onset of COVID-19 signs/symptoms

AND

Must **NOT** have shortness of breath **at rest or with exertion** as assessed by the investigator, respiratory failure, shock, or multi-organ dysfunction/failure (see definitions in Critical COVID-19 below)

Moderate COVID-19:

Must have **ONE or MORE** of the following:

- Shortness of breath **with exertion** as assessed by the investigator
- Respiratory rate ≥ 20 to < 30 breaths per minute
- Heart rate ≥ 90 to < 125 beats per minute

AND

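### The proportional odds model for the WHO 11-point scale omits Day 1 severity (mild, moderate), recorded before randomization for every participant, and so may give up some power

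*Combined protocol and SAP*

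**What the plan says.** Section 9.6.1 fits a proportional odds model to the WHO score and fixes its terms: "In addition to a term for treatment group, the model will include terms for the stratification factors specified Section 6.3.2". Table 5, footnote g, repeats this: "Proportional odds model includes terms for treatment and stratification factors specified in Section 6.3.2". In Part 2, Section 6.3.2 lists a single factor: "Time from symptom onset prior to the day of randomization (≤ 3 days, >3 days". Part 1 used symptom onset split at 5 days and increased-risk status. Severity is not a stratification factor in either part.

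Severity is nevertheless known before allocation. The Schedule of Activities (Section 1.3) requires: "COVID-19 severity categorization entered in IRT at randomization must be based on values obtained on Day 1 prior to randomization". Appendix 9 repeats the rule and admits only mild or moderate disease. The plan's one analytic use of severity is as a subgroup variable for the primary endpoint (Section 9.10).

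The endpoint is defined only after baseline: "Odds of a more favorable response on the WHO 11-point ordinal scale on Day 3, EOT, Day 10, Day 15, and Day 29". Section 9.1 places it among the key secondary endpoints. The score is derived; Section 9.4.1.1 says that component data "to support determination of the WHO 11-point ordinal score will be collected in eCRFs". No Day 1 score is named.

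**The concern.** In Part 2 the model has one binary covariate, and that covariate describes when symptoms began, not how ill the participant was. Severity plausibly predicts the score. Moderate disease in Appendix 9 can mean breathlessness on exertion or low-flow oxygen for COVID-19, and the WHO scale (Appendix 8) grades symptoms, need for assistance, oxygen and hospitalization. The first assessment, on Day 3, is close to baseline.

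Omitting a prognostic covariate from a proportional odds model pulls the common odds ratio toward 1 and lowers power. Because severity is not stratified either, neither the design nor the model deals with a chance imbalance between arms. What is at stake is some sensitivity on a key secondary endpoint that a value already in the database could supply.

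**Working it through.** **The plan's own figure.** None. The documents state no power, effect size or score distribution for the WHO scale.

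**Inputs from the documents.** About 775 per arm, 1:1 (Section 9.9.1); severity in two levels (Appendix 9); one-sided 2.5%, which the plan sets for the primary endpoint and which is borrowed here as a nominal level.

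**Inputs assumed.** Treatment odds ratio 1.3; prognostic odds ratio of severity 1.5, 2 or 3; 25% or 50% moderate; one marginal score distribution for Day 15 and one for Day 29. The only severity share in the documents is the Part 1 cap of about 50% (Sections 4.1 and 6.3.2). The symptom-onset term was left out of both models compared.

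**Method.** Fit logit P(Y ≤ k) = α_k + β·treatment, with and without γ·severity, by maximum likelihood to expected counts. Then:
- z = β/SE
- power = Φ(z − 1.96)
- equivalent sample size ratio = (z with severity / z without)²

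**One scenario in full** (Day 15, 50% moderate, prognostic odds ratio 3):
- Without severity: 0.2469/0.0922 = 2.678; power Φ(0.718) = 76.4%; odds ratio exp(0.2469) = 1.28.
- With severity: 0.2624/0.0931 = 2.818; power Φ(0.858) = 80.5%; odds ratio exp(0.2624) = 1.30.
- Sample size ratio: (2.818/2.678)² ≈ 1.11.
- SE ratio: 0.0931/0.0922 = 1.010, so the SE is slightly larger after adjustment.

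**All scenarios:**

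| Moderate | Prognostic OR | Day 15 power, without → with | Ratio | Day 29 power, without → with | Ratio |
|---|---|---|---|---|---|
| 25% | 1.5 | 80.7% → 81.1% | 1.01 | 74.8% → 75.2% | 1.01 |
| 25% | 2 | 79.8% → 81.0% | 1.03 | 73.7% → 74.9% | 1.03 |
| 25% | 3 | 77.8% → 80.8% | 1.08 | 71.0% → 74.2% | 1.08 |
| 50% | 1.5 | 80.6% → 81.1% | 1.01 | 74.6% → 75.1% | 1.01 |
| 50% | 2 | 79.3% → 80.9% | 1.04 | 73.2% → 74.7% | 1.04 |
| 50% | 3 | 76.4% → 80.5% | 1.11 | 70.1% → 73.7% | 1.09 |

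Across the table the SE of the log odds ratio is 0.1% to 2.1% larger with severity in the model. The power gain comes from the estimate moving away from 0, because the odds ratio is non-collapsible.

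**Cross-check by another method.** 4,000 simulated trials per scenario used a seven-category outcome, 775 per arm, treatment odds ratio 1.25, 45% in the worse group, and a rank test with and without stratification by a binary baseline factor. Power was 67% versus 68% at prognostic odds ratio 2 and 63% versus 68% at 3, about 4% and 11% more information. That agrees with the 50% moderate rows at Day 15.

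**Day 1 WHO score as a covariate.** Its components (swab, functional status, oxygenation) are scheduled on Day 1, so it could be derived. Entry requires a current symptom (Section 5.1) and no hospitalization (Section 5.2), which essentially leaves score 2 or 3. Assuming 1% to 10% at score 3 and a prognostic odds ratio of 2 or 3, the gain is 0.2% to 4% in equivalent sample size and at most 1.6 points of power.

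**The case against.** The strongest reply is that the plan adjusts for the randomization factors throughout its efficacy analyses, which is valid, prespecified and consistent. The WHO scale carries no multiplicity-controlled test and no stated power (Section 9.8), so a few points of nominal power change no decision that the plan defines. Severity may also be a weak predictor: a participant is moderate on a heart rate of 90 or a respiratory rate of 20 alone, while scores 0 to 3 turn on viral RNA, symptoms and need for assistance.

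Most of this stands. There is no error or contradiction, the prognostic strength is unknown, and the consequence is small. If severity and symptom onset are correlated, the planned term already captures part of the gain. It does not follow that the choice is only a matter of taste. Adjusting for a prognostic baseline factor raises power at no type I error cost, and the value is already collected.

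Four stronger readings are tempting and are not supported:
- **The estimate loses precision.** The SE does not fall with adjustment; what is lost is power.
- **The unadjusted odds ratio is biased.** It answers a marginal question rather than a conditional one.
- **A Day 1 WHO score is on file and should be the main covariate.** It is derivable, not recorded, and nearly constant. The documents give no rule for scoring a symptomatic but RNA-negative participant; scoring such people 0 would widen the spread.
- **The gain is large.** About 24% more information requires a prognostic odds ratio of 5, for which the documents offer nothing.

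**Conclusion.** The point holds as a minor improvement. The model omits a pre-randomization measure of illness that every participant has. If severity is prognostic, the cost is some power and a common odds ratio closer to 1, with type I error unaffected. Under the assumptions above, adding severity is worth about 1% to 11% in equivalent sample size, roughly 16 to 170 of 1550 participants (1550 × 0.01 and 1550 × 0.11), or about 0.4 to 4 points of power. The size rests entirely on the assumed treatment effect, prognostic strength, severity split and score distributions. If severity barely predicts the score, the gain is close to nothing.

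**What to change.** Add Day 1 severity (mild, moderate), as entered in the IRT, to the proportional odds model at each time point, in both Section 9.6.1 and Table 5, footnote g. Keep the model with stratification factors only as a sensitivity analysis. State that the reported odds ratio is conditional on severity. Leave the Day 1 WHO score out, or make it optional with a stated derivation rule.

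The change should be fixed before Part 2 is unblinded, since severity adjustment added later would look data-driven. Section 9 lets changes to non-confirmatory analyses be documented in the sSAP before unblinding, and this endpoint arguably qualifies. The cost is a line of wording and one extra model term; no new data are needed.
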